1.0 RESPONSIBLE PARTIES INVOLVED IN THE REGISTRY

A list of all responsible parties, such as laboratories, medical monitors, and contract research organizations, who are involved in the operations of the registry is filed in the Sponsor's Trial Master File. The names of the individuals and corresponding phone numbers who should be contacted regarding the conduct of the registry, adverse events, safety issues, and complaints are provided in the Site Investigator File.

2.0 STATEMENT OF COMPLIANCE

This registry will be conducted in accordance with specific provisions of the associated Institutional Review Board (IRB)/ Ethics Committee (EC) and in accordance with the ethical principles that have their origin in the Declaration of Helsinki, and that are consistent with Good Clinical Practice (GCP) and the applicable national and regional regulatory requirement(s).

4.0 PROTOCOL SUMMARY

Full Title	A Multicenter Observational Registry to Develop Ablation Parameter Guidance for Microwave Liver Ablation of Soft Tissue Lesions
Protocol Number	NEU_2017_04
Short Title	NOLA (NeuWave Observational Liver Ablation) Registry
IDE/IND number	N/A
Sponsor	NeuWave Medical, Inc.
Indication	Ablation (coagulation) of soft tissue in percutaneous, open surgical, and in conjunction with laparoscopic surgical settings, including the partial or complete ablation of non-resectable liver tumors.
Registry Article Description	
 • NEUWAVE Microwave Ablation System and Accessories (originally marketed as the “Certus 240 140 2.45GHz Ablation System and Accessories”; hereafter referred to as “NEUWAVE Microwave Ablation System”). • NEUWAVE Microwave Ablation System with Ablation Confirmation.
Registry Design	This is a multicenter, observational registry that follows patients for a total of 5 years from the date of the first liver ablation procedure with the NEUWAVE Microwave Ablation System.
Sample Size	N = up to 1500 patients ablated.
Registry Population	Patients with at least one soft-tissue liver lesion ablated with the NEUWAVE Microwave Ablation System or NEUWAVE Microwave Ablation System with Ablation Confirmation.
Geographic Areas	Starting at sites in the United States and expanding to regions where NEUWAVE Microwave Ablation Systems are available, including EMEA and Asia.
Registry Duration	Enrollment: ~2 years Follow up: 5 years
Procedure(s) Description	Patients who meet the eligibility criteria will undergo microwave ablation (MWA) with the NEUWAVE Microwave Ablation System with or without Ablation Confirmation of at least one soft-tissue liver lesion, in accordance with the study site’s standard-of-care (SOC) practices.
Primary Objective	The primary objective of this registry is to compile data that will be analyzed at various timepoints, to understand the impact of selected parameters on procedure/patient outcomes.

Primary Endpoints	
 • Technical success (perioperative endpoint) • Technique efficacy (short term endpoint) • Target lesion recurrence (local recurrence) rate (long term endpoint)
Secondary Endpoints	
 • Secondary efficacy rate • Regional recurrence rate at a separate location in the liver • Recurrence-free survival • Overall survival • Economic impact of ablation • Incidence of reportable Adverse Events/Serious Adverse Events (AEs/SAEs) • Numeric Pain Rating Scale • Quality of Life Questionnaires (QLQ-C30 and QLQ-HCC18)
Inclusion Criteria	
 1) Patients who underwent or are scheduled to undergo a microwave ablation of one or more liver lesions with the NEUWAVE Microwave Ablation System per the device's Instructions for Use (IFU). 2) Patients with signed informed consent (or waiver approved by IRB/EC) who are willing to comply with the assessment schedule, and willing to have data included in the database. 3) Patients ≥ 22 years old at the time of informed consent (or waiver approved by IRB/EC).
Exclusion Criteria	
 1) Patients with a life expectancy of less than 1 year, in the opinion of the treating physician. 2) Use of microwave ablation purely as a transection tool, rather than focused liver lesion ablation. 3) Patient is currently participating, or planning to participate, in another NeuWave/Ethicon-funded clinical trial or registry studying microwave ablation in the liver. Note: roll-over patients from previous NeuWave trials are permitted.
Safety Assessments	Patients will be assessed per the Schedule of Assessments for AEs that are procedure- or device-related and all SAEs.

Statistical Analysis	
Categorical variables will be summarized descriptively by frequencies and associated percentages. Continuous variables will be summarized descriptively by number of patients, mean, standard deviation, median, minimum, and maximum. Confidence intervals will also be provided for procedure-related variables.
 
Models will be built to explore the relationship between technical success, technique efficacy, and secondary efficacy rate, and ablation procedure, patient, and provider parameters. Time to event analyses will be used for target lesion recurrence rate, recurrence-free survival, and overall survival.

Interim Analysis	
There are no plans for interim analyses with intent to stop the registry early or to adapt the registry design or planned number of patients.

Determination, if DSMB required	
There will not be a DSMB utilized for this observational registry.

Schedule of Assessments Table:

Visit No.	Visit 1:	Visit 2			Visit 3	Visit 4	Visit 5	Visit 6	Visits 7 to 13	Visit 14/EOS	USV
Visit	Screening ²²	Ablation Day			Post-ablation	Post-ablation	Post-ablation	Post-ablation	Post-ablation	Post-ablation	Unsched. Visit ²³
Interval Windows	≤ 60 days pre-ablation	Day 0 = Ablation of target lesions			7 days to < 3 months	3 to < 6 months	6 to < 9 months	9 to < 12 Months	every 6 months	54 to 60 months	N/A
Registry Activity		pre	intra	post							
Eligibility criteria	X	X									
Informed consent / waiver	X										
Demographic information	X										
Patient parameters ¹	X										
Liver tissue assessment ²	X										
BCLC staging ³	X										
BMI	X										
ECOG performance ²⁵	X	X			X	X	X	X	X	X	
Child-Pugh Score ⁴ , ASA	X										
Coagulation tests ⁵	X				X	X	X	X	X	X	
Liver function tests ⁶	X				X	X	X	X	X	X	
Renal function tests ⁷	X				X	X	X	X	X	X	
Complete blood count ⁸	X				X	X	X	X	X	X	
Genetic marker levels: AFP, CA19-9, CEA ⁹	X				X	X	X	X	X	X	
Concomitant medications ¹⁰	X	X		X	X	X	X	X	X	X	X
Quality of life questionnaires ¹¹		X ²⁴			X	X	X	X			
Pain score ¹²		X ²⁴		X ²⁵	X						
Imaging ¹³	X	X	X	X	X	X	X	X	X	X	
Ablation procedure details ¹⁴			X	X							
Healthcare provider details ¹⁵				X							
Recurrence evaluation ¹⁶					X	X	X	X	X	X	X
Relevant concomitant procedures ¹⁷				X	X	X	X	X	X	X	X
Technical success evaluation ¹⁸				X							
Technique efficacy evaluation ¹⁹					X						
Economic impact data ²⁰			X	X							
Follow-up post-ablation treatment ²¹					X	X	X	X	X	X	X
AEs/SAEs			X	X	X	X	X	X	X	X	X

See List of Abbreviations Glossary in Section 22.2

1. Patient parameters, as listed in Section 19.1 Data Elements, subsection 2.
2. Liver tissue assessments, if available, including steatosis, fibrosis/ cirrhosis, liver stiffness, vascular invasion, micro satellite instability
3. If applicable: BCLC staging
4. If applicable: Child-Pugh Score
5. If applicable, per site SOC: Coagulation tests, including INR, PT, and APTT (or PTT).
6. If applicable, per site SOC: Liver function tests, including AST, ALT, GGT, albumin, direct and total bilirubin, and total protein.
7. If applicable, per site SOC: Renal function tests, including BUN, creatinine and electrolytes (sodium, potassium, chloride and bicarbonate).
8. If applicable, per site SOC: Complete blood count test, including differential cell count and platelet count.
9. If applicable, per site SOC: genetic markers include Alpha-fetoprotein (AFP), Carbohydrate antigen 19-9 (CA19-9), Carcinoembryonic antigen (CEA)
10. Record all relevant prior medications taken within 60 days prior to Visit 2 and all relevant concomitant medications taken throughout the registry. Relevant concomitant medications include: chemotherapy, immunotherapy, blood-thinning or coagulation, NSAIDs, those medications used to treat AEs, those used for hepatitis (if concurrently treating), and any others that are relevant in the opinion of the investigator. For post-ablation follow-up visits, relevant concomitant medications may be assessed over the phone, as needed.
11. Quality of Life questionnaires: EORTC QLQ-C30 and liver-specific QLQ-HCC18. The questionnaires may be administered over the phone, as needed.
12. Pain score, using the Numeric Pain Rating Scale. The questionnaire may be administered over the phone, as needed.
13. Use SOC imaging for all study visits.
14. Ablation procedure details, as listed in Section 19.1 of the protocol.
15. Healthcare provider parameters, as listed in Section 19.1 of the protocol.
16. SOC imaging as used at every follow-up visit to determine if there is local or regional recurrence of lesion(s). If there is a recurrence, determine soft tissue lesion details, via CT, MRI, PET, US, and/or X-ray. Scans will be submitted to the Sponsor (refer to NOTE 1).
17. Record only relevant concomitant procedures (i.e. liver or lesion-related). For post-ablation follow-up visits, relevant concomitant procedures may be assessed over the phone, as needed.
18. Technical success, defined as ablation of the target lesion(s) according to the protocol and covered completely, with an adequate margin, as defined by the physician performing the ablation (that is, the ablation zone completely overlaps or encompasses the target lesion plus an ablative margin), as assessed by CT, MRI, PET, US, and/or X-ray, immediately following the procedure. If patient has had any lesions ablated with NeuWave in the post-ablation follow-up visit period, assess Technical success following each ablation.
19. Technique efficacy, defined as ablation of the target lesion(s) according to the protocol and covered completely, with an adequate margin, as defined by the physician performing the ablation (that is, the ablation zone completely overlaps or encompasses the target lesion plus an ablative margin), as assessed by CT, MRI, PET, US, and/or X-ray, at Visit 3.
20. Economic impact data (as available), including the following: length of hospital stay, if applicable; number and types of probes used; and, ablation duration, defined as the time elapsed between first ablation probe puncture and removal of the last probe at the completion of the ablation.
21. Follow-up post-ablation treatment, including the number of successful repeat ablations, if applicable, and if patient has been hospitalized since the procedure. If patient has been re-ablated with NeuWave, record ablation procedure parameters as outlined in section 19.1, subsection 1. Record date of registry completion, when applicable.
22. When applicable, the Screening Visit may occur on the same day as the ablation procedure (Visit 2).
23. Record reason for unscheduled visit, as well as AEs (if applicable), and any updates to the relevant concomitant medications and relevant concomitant procedures.
24. Quality of Life and Pain Questionnaires may be administered up to 72 hours prior to the ablation procedure (Day 0).
25. Post-ablation Pain Score must be administered on the day of ablation (Day 0).
26. For Visit 1 through Visit 3, Eastern Cooperative Oncology Group classification (ECOG) performance status is required. After Visit 3, evaluate ECOG, if applicable per site SOC. ECOG may be assessed over the phone.

NOTE 1: All SOC scans of the abdomen/liver, including CT, MRI, and/or PET, taken at the following timepoints (Screening, Ablation Day, and throughout the 5-year follow-up period) should be submitted to the Sponsor through [REDACTED]. SOC Ultrasound scans of the abdomen/liver should also be submitted to the Sponsor, when on the Ablation Day or at any re-ablation visits. A subset of scans will be reviewed by the Central Review Committee to reduce the variability between investigators in assessing scans and to minimize potential bias.

NOTE 2: Patients rolling into this registry from a previous NeuWave trial will only have data collected in the Registry database starting from the time they consent to participate in the registry. Any data previously collected on roll-over patients will remain in the original database in which it was entered into.

ADMINISTRATIVE REQUIREMENTS

This registry is sponsored by NeuWave Medical, Inc. and will be conducted in all regions of the world under a single protocol approved by each participating site's Institution Review Board (IRB) / Ethics Committee (EC) prior to implementation. The Principal Investigator (PI) at each site must be qualified by education, experience, and training to perform the registry procedure and to assume responsibility for the conduct of this registry.

The Data Management and Biostatistics groups of Ethicon, Inc. will be responsible for the analysis of data from this protocol. An electronic data capture (EDC) system will be utilized by site personnel to transfer registry data from source records (the first point of clinical data capture) onto common electronic case report forms (eCRFs). This system is a web-based, secure electronic software application [REDACTED]. This system was designed, developed and maintained by [REDACTED] in a manner that is compliant with national and international Good Clinical Practice (GCP) data protection/data privacy and electronic record/electronic signature (e.g., 21 CFR Part 11) regulatory requirements.

Protocol Modifications

All protocol amendments must be issued by the Sponsor, signed and dated by the Investigator, and should not be implemented without prior IRB/EC approval, except where necessary to eliminate immediate hazards to the patients or when the change(s) involves only logistical or administrative aspects of the registry (e.g., change in monitor, change of telephone number, etc.). The Investigator will report the protocol amendments to the IRB/EC as per their local requirements.

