7.0 REGISTRY DESIGN

7.1 Overall Registry Design and Plan – Description

This is a multicenter, observational registry that follows patients for a total of 5 years from the date of the first liver ablation procedure with the NEUWAVE Microwave Ablation System. The data gathered from participating sites will be available to be analyzed to develop ablation parameter guidance for ablation approaches under varying patient liver tissue conditions and liver lesions.

This is an “umbrella registry,” which was included as an optional component in other NEUWAVE studies; hence, data from consenting patients who are or will be enrolled in other NEUWAVE soft tissue liver lesion ablation studies will be included in this registry. All other patients will be enrolled and followed prospectively, enrolled retrospectively with prospective, longitudinal follow up, or enrolled retrospectively with all retrospective follow up.

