7.4 Exclusion Criteria

1. Patients with a life expectancy of less than 1 year, in the opinion of the treating physician.
2. Use of microwave ablation purely as a transection tool, rather than focused liver lesion ablation.

3. Patient is currently participating, or planning to participate, in another NeuWave/Ethicon-funded clinical trial or registry studying microwave ablation in the liver. Note: roll-over patients from previous NeuWave trials are permitted.

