13.2 Reporting Adverse Events

All procedure-related and device-related AEs (non-serious) and all SAEs from the time of the first probe placement through study completion (Visit 14), or to the time of early withdrawal of the study, must be reported in the AE eCRF. The Investigator will evaluate the severity of the event and its relatedness to the registry device or procedure.

The Investigator is required to report all applicable non-serious AEs to the Sponsor within 2 weeks of becoming aware of the adverse event(s). All SAEs are to be reported as soon as possible, but no later than 72 hours after becoming aware of the event, regardless of relationship to the device or study procedure.

The study site will report applicable AEs and all SAEs to the Sponsor by entering the event into the EDC system via the Adverse Event eCRF, which will trigger an automated email to the Sponsor. Additional information, including the Investigator's assessment, may be added to the eCRF later. Any necessary medical management of the event will be recorded in the patient's medical record/source document. If the Sponsor requires supporting documentation or other information, the Sponsor will contact the study site.

Data related to AEs and SAEs will be collected until event resolution, until the event is considered stable, or until all attempts to determine the resolution of the event are exhausted. All AEs and SAEs that are unresolved at study completion (or early termination) will be recorded as ongoing at study end.

In addition, the following information should be recorded:

- Onset date
- Resolution date or date of death
- Action taken
- Event status (ongoing at registry end or resolved)
- Relationship of AE to the ablation device used in the registry
- Relationship of AE to the registry procedure
- Indication of seriousness.
- Was AE anticipated or not (only for serious, device-related AEs)

The report of an AE or SAE by a site does not constitute an admission that registry personnel or the user facility (hospital/clinic) caused or contributed to the event. The site is responsible for submitting AEs to the reviewing IRB/EC, per their IRB/EC procedures.

For retrospectively enrolled patients, the site should review patient medical records (i.e. through chart review) to look for reportable AEs/SAEs. Collection of AE data and reporting requirements will be the same for retrospective events, however, Sponsor reporting timelines do not apply.

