1.2 Study Design

This is a multicenter, observational registry that follows patients for a total of up to 5 years from the date of the first liver ablation procedure with either the NEUWAVE Microwave Ablation System or the NEUWAVE Microwave Ablation System with Ablation Confirmation.

This is an “umbrella registry,” which was included as an optional component in other NEUWAVE studies; hence, data from consenting patients who are or will be enrolled in other NEUWAVE soft tissue liver lesion ablation studies will be included in this registry. All other patients will be enrolled and followed prospectively, enrolled retrospectively with prospective, longitudinal follow up, or enrolled retrospectively with all retrospective follow up.

2 Treatment Assignment

This is a single-arm registry where all enrolled patients will be ablated using the NEUWAVE Microwave Ablation System as part of the site’s SOC treatment or per protocol for those patients who are also enrolled in other NEUWAVE studies.

3 Randomization and Blinding Procedures

As this is a single-arm registry, no randomization will occur, and no blinding procedures are required.

4 Interval Windows

Interval windows are provided in the Schedule of Assessments section of the study protocol. No additional windows are planned for analysis purposes.

5 Levels of Significance

No levels of significance are specified as no specific hypotheses about any of the outcomes of interest are being formulated or tested. Two-sided 95% confidence intervals (CI) will be estimated for specific endpoints for descriptive purposes only.

6 Analysis Sets

All Enrolled Set (AES): Consists of subjects who signed informed consent form or retrospectively enrolled with a waiver for signing informed consent form. The AES will be used for disposition of study subjects.

Full Analysis Set (FAS): FAS Consists of subjects who met inclusion/exclusion criteria and to whom the NeuWave Ablation device was utilized during procedure. Primary and secondary endpoints will be analyzed using FAS.

Safety Analysis Set (SAF): SAF Consists of subjects who met inclusion/exclusion criteria and to whom the NeuWave Ablation device was utilized during procedure. Safety endpoints will be analyzed using SAF.

7 Sample Size Justification

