Overall survival rate will be estimated at 3-month, 6-month, and up to 60-month follow up using Kaplan-Meier's method. Two-sided 95% CI will be estimated for overall survival rate.

Scores from the EORTC QOL questionnaires and Numeric Pain Rating Scales will be summarized with methodology consistent to the recommendations of the specific survey. Economic impact of ablation by capturing procedure-related items will be summarized with descriptive statistics.

Incidence of adverse events (AEs) (SAEs) that are deemed at least unlikely related to the procedure or device and all serious adverse events (SAEs) from the start of the ablation procedure through the end of the study will be summarized by MedDRA system organ class (SOC) and preferred term (PT).

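### Procedure-period adverse event incidence will be biased low to the extent that the safety set includes roll-over patients who joined the registry after their ablation

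*Protocol*

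**What the plan says.** **Who is in the registry.** Protocol 7.1 includes "data from consenting patients who are or will be enrolled in other NEUWAVE soft tissue liver lesion ablation studies". SAP 1.2 repeats this and says that all other patients are enrolled prospectively, "enrolled retrospectively with prospective, longitudinal follow up, or enrolled retrospectively with all retrospective follow up". Exclusion criterion 3 (Protocol 7.4) bars concurrent participation in another sponsor-funded liver ablation study, but adds: "Note: roll-over patients from previous NeuWave trials are permitted".

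**When their data start.** NOTE 2, below the Schedule of Assessments in Protocol Section 4.0, says that roll-over patients "will only have data collected in the Registry database starting from the time they consent to participate in the registry". It continues: "Any data previously collected on roll-over patients will remain in the original database in which it was entered into".

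**What is counted.** AE incidence is secondary endpoint 6 (Protocol 6.3, SAP 8.4.2). Under SAP 8.6, events "from the start of the ablation procedure through the end of the study will be summarized" by system organ class and preferred term. Protocol 13.2 requires reporting from first probe placement and makes no exception for roll-overs. For chart-review patients it says: "For retrospectively enrolled patients, the site should review patient medical records (i.e. through chart review) to look for reportable AEs/SAEs". It then applies the same collection requirements to them and waives only the sponsor reporting timelines.

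**Who is in the denominator.** In SAP Section 6 the safety set (SAF) is defined by eligibility and use of the device. "Safety endpoints will be analyzed using SAF".

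**What adjustment is planned.** SAP 8.13 separates AEs by relatedness and seriousness only. The subgroups in SAP 8.8 cover the primary endpoints only. SAP 8.7 plans no sensitivity analysis, and SAP 8.11 no imputation.

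**The concern.** Taken together, these rules describe a risk period that opens at ablation, a denominator that does not depend on that period having been observed, and one class of patient whose record may open only later. For such a patient, an absence of procedure-period events in the registry means that nobody recorded them there. It does not mean that none occurred. Counting the patient as event-free can only pull the incidence down.

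Most AEs tied to an ablation would be expected around the procedure, and AE incidence is a listed secondary endpoint. A diluted rate would make the device look safer than the observed patients show. Any confidence interval would be centred on the diluted value and would be too narrow, because it takes credit for patients who carry no information on that period. Neither document describes a link to the original trial databases, and no planned table in the SAP text would let a reader see the dilution.

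**Working it through.** The plan states no AE rate, no mix of enrolment types and no sample-size calculation, so there is no figure to reproduce. The check is a dilution identity with assumed inputs.

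**Inputs**
- *p*: true procedure-period incidence. Assumed, 5% to 20%.
- *f*: share of the SAF that are roll-overs who consented after the procedure period. Not given; shown from 5% to 20%.
- *N* = 1500, for illustration. The Protocol Summary gives this as a maximum and Protocol 7.2 as a minimum.
- Roll-overs are taken to have the same true incidence as other patients, and all other patients to have full capture.

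**Formula.** Reported incidence = *p* × (1 − *f*), so the relative bias is −*f* whatever the value of *p*.

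**Results for *p* = 10%** (Clopper-Pearson 95% intervals)

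| *f* | As planned | Denominator limited to observed patients |
|---|---|---|
| 5% | 142/1500 = 9.5% (8.0 to 11.1) | 142/1425 = 10.0% (8.5 to 11.6) |
| 10% | 135/1500 = 9.0% (7.6 to 10.6) | 135/1350 = 10.0% (8.5 to 11.7) |
| 20% | 120/1500 = 8.0% (6.7 to 9.5) | 120/1200 = 10.0% (8.4 to 11.8) |

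In the 5% row, the expected 142.5 events are rounded down. The last column returns 10% by construction, given equal underlying incidence.

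**When the interval misses the true value.** At N = 1500 the interval first excludes *p* at these shares:
- *p* = 5%: *f* of about 22% (58/1500, upper limit 4.97%).
- *p* = 10%: *f* of about 15% (127/1500, upper limit 9.99%).
- *p* = 20%: *f* of about 10% (269/1500, upper limit 19.97%).

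Below these shares the estimate is still low, but the interval covers the truth.

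**Chart-review patients, conditional only.** Let *g* be their share and *s* their capture relative to prospective patients. The identity becomes *p* × [(1 − *f* − *g*) + *g* × *s*], with relative bias −*f* − *g*(1 − *s*). With *f* = 0, *g* = 50% and *s* = 0.8, the bias is −0.5 × 0.2 = −10%. With *s* = 1 it is zero. Nothing in the documents fixes *g* or *s*.

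**The case against.** **The affected share may be small or nil.** Protocol 7.1 describes the registry as an optional part of other sponsor studies and includes patients yet to be enrolled in them. Protocol 17.3 speaks of patients being ablated under those protocols. A patient who consents to the registry at entry to the parent study loses nothing under NOTE 2. This stands, and it is why the point is conditional. It does not dispose of the point: exclusion criterion 3 expressly admits roll-overs from previous trials, and for such patients the first ablation would normally lie in the earlier trial.

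**SAF membership is unclear.** If Day 0 data are not in the registry database, the SAP does not say how a late-consenting roll-over would be identified as treated. That is a fair gap to note. On the definition as written, though, the patient qualifies, and nothing removes those without observed procedure data.

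**Chart review.** A reader might infer that retrospective patients are also under-counted, particularly for mild events. The documents do not show this, since Protocol 13.2 sets the same collection requirements for them. Capture limited to what the record holds is plausible, but it remains an assumption.

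**Events judged unlikely to be related are counted as related** (Protocol 13.1), which raises related-event counts. That is part of how the endpoint is defined. It does not recover events held in another database.

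**Other limits.** The table shells are a separate document (SAP Section 10), so one can say only that the SAP text specifies no split by enrolment type. The intervals for AEs of interest are optional (SAP 8.13), no hypothesis is tested, and all reported AEs will be listed. These points lower the stakes but leave the incidence itself uncorrected.

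**Conclusion.** The point holds in conditional form. Followed as written, the plan places roll-overs who consented after ablation in the safety denominator with no means of contributing a procedure-period event. The resulting bias is downward, with relative size equal to their share: 10% true incidence reads 9.0% at a 10% share and 8.0% at a 20% share. This assumes that the whole procedure period precedes their consent, that their original-trial AEs are not brought in, and that their underlying incidence matches that of other patients. Events after consent are still collected, so the loss is confined to the earlier period.

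A reader might go further and conclude that all the pooled AE rates are certainly too low. The documents do not support that, because they give neither the roll-over share nor the timing of consent. Nor do they support adding a chart-review loss to the estimate. For example, take a true 20% incidence, 5% to 20% roll-overs, and 20% to 40% chart-review patients with 50% to 80% capture. The pooled rate then runs from 0.20 × (0.40 + 0.40 × 0.5) = 12.0% to 0.20 × (0.75 + 0.20 × 0.8) = 18.2%. About half of that shortfall comes from the capture assumption. Without it the range is 0.20 × 0.80 = 16.0% to 0.20 × 0.95 = 19.0%, and the roll-over share is still assumed.

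**What to change.** 1. Reconcile NOTE 2 with Protocol 13.2 and SAP 8.6 and 8.13 for roll-over patients, and state whether AEs from the original trial databases will be integrated into the registry analysis.
2. If they will not be, limit the denominator for procedure-period AE incidence, and for any intervals, to patients whose registry data cover the time from first probe placement. Report how many roll-overs are left out.
3. In SAP 8.13, tabulate AEs and SAEs by enrolment type: prospective, retrospective with prospective follow-up, fully retrospective, and roll-over. This would also show whether chart-review patients have lower recorded rates, without assuming it.

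The cost is SAP wording, a few extra table columns and a somewhat smaller denominator: 1350 instead of 1500 at a 10% share. Steps 2 and 3 need no new data collection. Integration under step 1 would need access to the earlier trials' AE data. The restricted rate represents all treated patients only if the excluded roll-overs are similar to the rest, which is why their number should be reported.
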